7.3 Study procedures

Patients will be in follow up for 6 months. There are 4 site visits. T0 to collect baseline parameters after which the intervention is performed. T1 at one month post intervention. T2 at 3 months post intervention at which the primary endpoint is collected. T3 at 6 months post intervention.

Table 1 (Appendix E) provides an overview of all study procedures per follow up moment. There is a distinction between study procedures at site and study procedures at home.

7.4 Withdrawal of individual subjects

Subjects can leave the study at any time for any reason if they wish to do so without any consequences. The investigator can decide to withdraw a subject from the study for urgent medical reasons.

7.5 Premature termination of the study

Premature termination is only possible:

- if the judgement of the competent medical research ethics committee that has assessed the study is irrevocably revoked;
- if a reasonable case can be made for terminating the study in the interests of the health of the research subjects;
- if it transpires that continuation of the study cannot serve any scientific purpose, and this is confirmed by the medical research ethics committee that has issued a positive decision on the study;
- if one of the parties or the funder has been declared insolvent or a bankruptcy/winding-up petition has been filed in respect of one of the parties or the financier, or one of the parties or the financier is dissolved as a legal entity;

Cocogen Trial

- if the principal investigator is no longer capable of performing the tasks of the principal investigator, and no replacement agreeable to both parties can be found;
- if one of the two parties fails to comply with the obligations arising from the agreement and, provided compliance is not permanently impossible, this compliance has not taken place within thirty days of the defaulting party receiving a written request to comply, unless failure to comply is not in reasonable proportion to the premature termination of the study;
- if circumstances beyond the control of the sponsor, investigator or funder make it unreasonable to require the study's continuation.

Cocogen Trial

8. SAFETY REPORTING

8.1 Temporary halt for reasons of subject safety

In accordance to section 10, subsection 4, of the WMO, the sponsor will suspend the study if there is sufficient ground that continuation of the study will jeopardise subject health or safety. The sponsor will notify the accredited METC without undue delay of a temporary halt including the reason for such an action. The study will be suspended pending a further positive decision by the accredited METC. The investigator will take care that all subjects are kept informed.

8.2 AEs, SAEs and SUSARs

8.2.1 Adverse events (AEs)

Adverse events are defined as any undesirable experience occurring to a subject during the study, whether or not considered related to the investigational intervention. All adverse events reported spontaneously by the subject or observed by the investigator or his staff will be recorded.

The potential risks to subjects in which a radiofrequency neurotomy procedure is performed, regardless of the treatment modality, may include the following, all of which are anticipated adverse events that have been identified as possible complications of procedures involving lesioning of nervous tissue:

- Infection,
- Damage to collateral nervous tissue,
- Increased pain,
- Failure of technique,
- Superficial burns,
- Damage to collateral tissue (i.e., bruising or hematoma),
- Deafferentation dysesthesia
- Paralysis
- Allergy

Subjects should be instructed to contact the investigator immediately if an AE occurs. At each visit, the investigator should further query the subject to determine if any new adverse events have occurred. Adverse events will be assessed and reported from the time the subject signs consent until study exit according to the following procedure.

Cocogen Trial

The investigator will assess the severity of each AE based on the following definitions:

Severity	Definition
Mild	An AE in which the subject is aware of signs or symptoms, but which does not
	interfere with the subject's usual activities of daily living, or is transient and
	resolves without treatment or sequelae.
Moderate	A sign or symptom which interferes with the subject's usual activities of daily
	living or requires treatment.
Severe	Any event listed as serious adverse event.

For each AE, the investigator will assess the causality/relationship to the received treatment according to the following criteria:

Relatedness	Definition
Possible	The association of the AE with the test article is unknown; other etiologies are also possible.
Probable	A reasonable temporal sequence of the AE with test article administration exists and based upon the medical professional's clinical experience, the association of the AE with the test article seems likely.
Definite	A causal relationship exists between the received treatment and the AE, and other conditions (e.g., concomitant illness, progression or expression of the disease state, reaction to concomitant medications) do not appear to explain the AE.

All AEs must be recorded in the subject's medical record and the appropriate eCRF. The description of the AE will identify the date of onset, date of remission, severity, causal relationship to the study treatment, action taken along with the results of any diagnostic procedures or laboratory tests, all treatments that were required and the outcome of the AE.

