8.2.2 Serious adverse events (SAEs)

A serious adverse event is any untoward medical occurrence or effect that

- results in death;
- is life threatening (at the time of the event);
- requires hospitalisation or prolongation of existing inpatients' hospitalisation;
- results in persistent or significant disability or incapacity;
- any other important medical event that did not result in any of the outcomes listed above due to medical or surgical intervention but could have been based upon appropriate judgement by the investigator.

Cocogen Trial

- An elective hospital admission will not be considered as a serious adverse event.

Sites will be instructed to follow their normal routine processes for adverse event reporting. However, serious adverse events will be specifically monitored for. The sponsor will report the possible, probable or definite related SAEs through the web portal 'ToetsingOnline' to the accredited METC that approved the protocol, within 7 days of first knowledge for SAE's that result in death or are life threatening followed by a period of maximum of 8 days to complete the initial preliminary report. All other SAEs will be reported within a period of maximum 15 days after the sponsor has first knowledge of the serious adverse events. All reported SAE's will be mentioned to the accredited METC that approved the protocol in a yearly summary.

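### The adverse-event scales in 8.2.1 have no level for an unrelated event and define Severe as serious, so the SAE reporting filter in 8.2.2 excludes nothing and the intensity of non-serious events is capped at Moderate

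*Protocol*

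**What the plan says.** **Scope.** Protocol 8.2.1 defines an AE as any undesirable experience during the study, "whether or not considered related to the investigational intervention". Events are collected from the signing of consent until study exit.

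**Relatedness.** "For each AE, the investigator will assess the causality/relationship to the received treatment according to the following criteria". The table that follows has three levels: Possible, Probable and Definite. Possible is defined as "The association of the AE with the test article is unknown; other etiologies are also possible".

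**Severity.** "The investigator will assess the severity of each AE based on the following definitions". There are three grades:
- Mild covers events that do not interfere with daily activities. It has a second branch, opening "or is transient and", for events that resolve without treatment or sequelae.
- Moderate is "A sign or symptom which interferes with the subject's usual activities of daily" living, or one that needs treatment.
- Severe is "Any event listed as serious adverse event".

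The text after the tables makes severity and causal relationship recorded items for every AE, in the medical record and the eCRF.

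**Reporting.** Section 8.2.2 defines a serious event by death, threat to life, hospitalisation, disability or incapacity, or another important medical event in the investigator's judgement. It then states: "The sponsor will report the possible, probable or definite related SAEs" to the ethics committee, within set time limits.

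**Endpoint.** Sections 7.1.2 and 9.2 list the amount of AEs and/or SAEs as a secondary parameter, reported as a difference between groups with exploratory testing.

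**The concern.** A causality scale applied to all events needs a level for those that the treatment did not cause. Without one, the investigator must either use a level whose definition does not fit or leave the item empty, and an empty item cannot be told apart from missing data. A reporting filter built on that scale then has nothing to filter.

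Intensity and seriousness are different properties. Intensity is how strong the symptom is. Seriousness is what the event led to. When the top intensity grade is defined by seriousness, the grade adds nothing to the SAE flag at the top and does not separate intense from modest events below it. That matters here because 8.2.1 lists increased pain and deafferentation dysesthesia among the anticipated harms of the procedure, and such events may well be non-serious.

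These are data-capture rules. If a rating is not collected during the trial, no later analysis document can restore it.

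**Working it through.** There is no figure in the plan to reproduce and no arithmetic beyond counting levels. The check sets the provisions side by side.

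**Step 1: do unrelated events enter the scale?** Yes. The AE definition in 8.2.1 includes them and the causality rating is required for each AE. The protocol also makes such events foreseeable:
- Collection starts at consent. By 10.2, consent is signed before treatment and is followed by the baseline measurement. An event in that interval cannot be due to the procedure.
- Sections 4.2 and 5.2 allow other therapies during follow-up, and 4.2 names surgery. Appendix E collects AEs up to 12 months. An event plainly due to another intervention or illness is therefore in scope.

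**Step 2: does any level fit an unrelated event?** There are three levels, and none means unrelated. Possible describes an unknown association, so an event whose cause is known to lie elsewhere does not meet even the lowest definition. No other section supplies a further level.

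**Step 3: what does the filter in 8.2.2 exclude?** It names Possible, Probable and Definite, which is three of the three levels. An SAE rated on the printed scale therefore always passes. Yet a rule that selects related SAEs presupposes that some are not. The two sections do not fit together.

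**Step 4: which severity grades can a non-serious event receive?** Severe requires the event to be an SAE, so two of three grades remain, Mild and Moderate. Moderate has no upper limit: it runs from slight interference with daily activities to intense pain needing treatment. An intense event that is transient and resolves untreated also meets the second branch of Mild. The cap is therefore at most Moderate, not always Moderate.

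**Step 5: which severity grade does an SAE receive?** Severe in every case. An SAE of modest intensity, such as a brief unplanned admission for observation, is graded the same as an intense one.

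**Step 6: which planned outputs depend on these scales?** The endpoint in 7.1.2 and 9.2 counts AEs and SAEs. Neither relatedness nor severity enters that count, so it is unchanged. The scales do govern the SAE filter in 8.2.2 and any table that breaks AEs down by relatedness or grade.

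**The case against.** The strongest reply is that little of consequence rests on these scales. Several parts of it stand.

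- **No planned analysis uses them.** The endpoint is a count of all events, and the same scales apply in both arms. A reader might infer that the comparison of AEs between techniques is spoiled or biased. The documents do not support that.
- **No related-event rate is planned.** A reader might infer that the pilot will hand inflated related-event rates to the future trial. The objectives (section 2) and the sample size section (4.4) list treatment effects, inclusion rates, comparability of populations and initial cost-effectiveness as what the pilot is to supply. Overstatement would arise only if such rates were tabulated, and its size could not be derived from the protocol.
- **Intensity of harm is not lost altogether.** A reader might infer that the pilot cannot compare the intensity of harm between techniques. But 7.1.1 collects NRS scores at each visit and a four-day pain diary, 7.1.2 tracks medication use, and 8.2.1 records dates, action taken, treatments and outcome for each AE.
- **A disabling event may itself be serious.** Section 8.2.2 counts significant disability or incapacity as serious, so a truly disabling flare could be graded Severe. The gap concerns intense events that are neither disabling nor otherwise serious.
- **A filter that excludes nothing errs toward over-reporting.** In a study of 48 patients that is an administrative burden, not a loss of safety information.

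One further argument holds only in part. The table could be read as grading degrees of relatedness, with unrelated events left ungraded, and the eCRF is not shown. It is therefore too strong to say that every AE will in practice be recorded as related. But 8.2.1 asks for a rating on each AE and provides no way to record that an event is unrelated, so this reading does not remove the gap.

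**Conclusion.** The point holds as a defect in two data-capture rules. The relatedness scale has no level for events that the protocol requires to be rated, and the SAE filter in 8.2.2 names all of its levels, so it excludes no rated SAE. Severity is merged with seriousness at the top of the scale, so a non-serious event can reach at most Moderate and every SAE is Severe.

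The reach is limited. The planned AE and SAE counts are unaffected, no directional bias between arms is shown, and no efficacy, cost or sample size result is touched. What is affected is the reporting filter and any tabulation by relatedness or severity. How many events would be misplaced cannot be stated, because the protocol gives no expected number of unrelated or of intense non-serious events.

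The conclusion assumes that the relatedness table is complete as printed. It has a header and three full rows, and 8.2.2 names the same three levels. It also assumes that the eCRF follows the protocol's scale.

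**What to change.** 1. In the relatedness table of 8.2.1 and in the eCRF, add a Not related level, and an Unlikely level if wanted.
2. In 8.2.2, align the reporting filter with the revised scale, so that the levels it names are a true subset. If Unlikely is added, state on which side of the filter it falls.
3. In the severity table of 8.2.1, define Severe by intensity, for example as preventing usual daily activities. Word Mild and Moderate so that one event cannot meet both.
4. Record seriousness as a separate yes/no item for each AE, using the existing criteria in 8.2.2.
5. If AEs are tabulated by relatedness or severity, show relatedness, severity and seriousness separately by arm.

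The cost is one added level, one or two reworded definitions and one eCRF item. It needs no extra visits, patients or measurements, but it has to be in place before events are rated.

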8.2.2 Serious adverse events (SAEs)

A serious adverse event is any untoward medical occurrence or effect that

- results in death;
- is life threatening (at the time of the event);
- requires hospitalisation or prolongation of existing inpatients' hospitalisation;
- results in persistent or significant disability or incapacity;
- any other important medical event that did not result in any of the outcomes listed above due to medical or surgical intervention but could have been based upon appropriate judgement by the investigator.

Cocogen Trial

- An elective hospital admission will not be considered as a serious adverse event.

Sites will be instructed to follow their normal routine processes for adverse event reporting. However, serious adverse events will be specifically monitored for. The sponsor will report the possible, probable or definite related SAEs through the web portal 'ToetsingOnline' to the accredited METC that approved the protocol, within 7 days of first knowledge for SAE's that result in death or are life threatening followed by a period of maximum of 8 days to complete the initial preliminary report. All other SAEs will be reported within a period of maximum 15 days after the sponsor has first knowledge of the serious adverse events. All reported SAE's will be mentioned to the accredited METC that approved the protocol in a yearly summary.

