4.2 Inclusion criteria

In order to be eligible to participate in this study, a subject must meet all of the following criteria:

- Age ≥ 18 years
- Able to understand the informed consent form and provide written informed consent and able to complete outcome measures.
- Chronic anterior knee pain (> 12 months) with an NRS > 4 on most or all days for the index knee either constantly or with motion.
- Unresponsive to conventional treatments continued during 12 months including physiotherapy, oral analgesics or intra-articular infiltrations.
- Radiologic confirmation of arthritis of OA grade of 2 (mild), 3 (moderate) or 4 (severe) noted within 6 months for the index knee according the Kellgren Lawrence criteria (27) diagnosed by an independent radiologist with experience in musculoskeletal imaging on Rx or MRI (28) or patients with total knee arthroplasty of the index knee with a negative orthopaedic workout.
- Other therapies (including surgical interventions) for pain in the index knee are allowed for the period of the study follow up as long as they are documented. This is necessary to correctly estimate the costs in the cost effectiveness analyses. Allowing patients to receive additional treatments will also improve the protocol compliance.
- Agree to provide informed consent and to comply with the requirements of this protocol for the full duration of the study

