- The change in health-related quality of life, measured by the change in EQ-5D-5L, between baseline and 6 and 12 months post intervention. (41) The EQ-5D-5L is a patient-reported generic measure of HRQoL comprising five dimensions: mobility, self-care, usual activities, pain/discomfort and anxiety/depression. Responses to the 5 items (one for each dimension) result in a patient's health state that can be transformed into a utility score ranging between 0 (death) and 1 (full health), representing the quality of life of the health state. (41). The EQ-5D-5L is assessed at baseline and at 1, 3, 6 and 12 months post intervention.
- Change in characteristic attitudes and symptoms of depression from baseline to 3, 6 and 12 months post intervention. This will be measured by the change in Hospital Anxiety and Depression Scale (HADS) and in Pain Catastrophizing Scale (PCS) from baseline to 6 and 12 months. (42, 43) HADS is developed to detect anxiety and depression in patients with physical health problems. The questionnaire consists of 14 items: 7 items to measure anxiety and 7 items to measure depression. The PCS is often used in clinical settings to measure catastrophic thinking related to pain. The 13 item questionnaire consists of 3 subscales (magnification, rumination and helplessness) and asks patients to

Cocogen Trial

reflect on past painful experiences and to indicate the degree on which they experiences each of 13 thoughts of feelings on a 5- point scale (0 not at all and 4 all the time).

- Amount of Adverse Events and/or Serious Adverse Events. Active capture during each site visit to assess specific symptoms and adverse events that are relevant to chronic knee pain or RF treatment.

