- Costs in both intervention groups. Costs include health care related costs (e.g. intervention cost, medication), costs to patients and family (e.g. travel costs, out-of-pocket payments), and costs due to lost productivity. Complete individual level hospital resource use data (e.g. surgical intervention, diagnostic procedures, hospital admissions, outpatient clinic visits) will be measured using medical records and by means of a self-developed questionnaire to be completed by patients, based on the iMTA Medical Consumption Questionnaire as recommended in the Dutch guideline for economic evaluation. (44) The questionnaire will have a recall period of 3 months and will be administered repeatedly at baseline, 3, 6 and 12 months post intervention. The Dutch manual for costing research will be used to determine prices for each volume of resource use. (45)
- Cost-effectiveness will be expressed using incremental cost-effectiveness ratios (e.g. incremental cost per QALY, incremental cost per reduced point on the pain score, and incremental costs per additional treatment success). QALYs (Quality Adjusted Life Years) will be calculated by multiplying life years with the health-related quality of life during these life years as measured by the EQ-5D-5L.
- At 12 months in the osteoarthritis group, we ask if a total knee arthroplasty is performed and if so at which timepoint.
- All used questionnaires to retrieve the above mentioned outcome parameters can be found in Appendix D.

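### The SAE exemption for elective admissions does not separate admissions planned before consent from admissions scheduled because of a new or worsened event

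*Protocol*

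**What the plan says.** Protocol section 8.2.2 lists five routes to seriousness. One is death. Three others are "is life threatening (at the time of the event", "requires hospitalisation or prolongation of existing" inpatient stay, and "results in persistent or significant disability or incapacity". The fifth is an important medical event, left to the investigator's judgement, where intervention prevented one of the other outcomes. A closing bullet then states: "An elective hospital admission will not be considered as a serious adverse event". It carries no condition on when the admission was planned or why.

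Three other places depend on this definition or bear on it:

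- Section 8.2.1 defines the Severe grade as "Any event listed as serious adverse event". Moderate covers an event that interferes with daily activities or needs treatment.
- Section 7.1.2 makes "Amount of Adverse Events and/or Serious Adverse Events" a secondary outcome, and section 9.2 includes it in the exploratory between-group comparison.
- Section 4.2 says: "Other therapies (including surgical interventions) for pain in the index knee are allowed for the period of the study follow up", provided they are documented. Scheduled surgery on the study knee is therefore foreseeable during follow-up.

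**The concern.** The exemption turns only on how an admission was scheduled. Its natural purpose is to keep surgery already on a waiting list, or planned care for an unchanged condition, out of the SAE count. As worded it also covers an admission arranged because something went wrong after RF treatment. Section 8.2.1 names infection, increased pain, damage to neighbouring nerve or other tissue, and deafferentation dysesthesia as possible complications. If one of these led to a booked rather than an emergency admission, the bullet could remove it from the SAE class.

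SAE status controls what the ethics committee sees. Section 8.2.2 sends SAEs judged at least possibly related to the METC on a fixed clock and summarises reported SAEs yearly. The progress report in section 11.3 likewise lists serious events. There is no second route: section 8.5 sets up no DSMB, and section 8.3 marks the annual safety report as not applicable.

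**Working it through.** No arithmetic applies. The check sets the rules side by side and follows four cases through them.

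**Step 1: what the bullet changes.** Of the five criteria in section 8.2.2, only hospitalisation depends on an admission. The exemption can therefore narrow only that criterion; the other four stand however an admission is scheduled.

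**Step 2: four cases under the literal text.**

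| Case | Hospitalisation criterion | Other criteria | Class | Highest severity grade | Reported to METC as SAE |
|---|---|---|---|---|---|
| A. Knee operation booked before consent, condition unchanged | exempt | none | not an SAE | not applicable (no new event) | no |
| B. RF-related event, emergency admission, no other serious feature | met | none | SAE | Severe | yes |
| C. Same event as B, but the admission is scheduled | exempt | none | AE only | Moderate | no |
| D. RF-related nerve damage with lasting disability, scheduled admission | exempt | disability met | SAE | Severe | yes |

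Case A is handled sensibly. Case D shows that the other criteria still work. The problem is the contrast between B and C: the clinical event is the same and only the booking of the bed differs, yet the class, the severity ceiling and the reporting all change.

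**Step 3: what is lost in case C.** The event has no life-threatening feature, so in case B it would fall under the 15-day reporting limit and then appear in the yearly summary. In case C both are lost, and the event is absent from the SAE count in section 7.1.2. Because section 8.2.1 reserves Severe for SAEs, the severity grade cannot show the difference either.

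**Step 4: what is kept in case C.** Section 8.2.1 requires every adverse event to be recorded, related or not. It also requires the severity, causality, treatments needed and outcome to be described. The event therefore remains in the AE data and in the AE part of the secondary outcome. The investigator may also judge it an important medical event, which would restore SAE status, but the text does not require this.

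**The case against.** The strongest reply is that the bullet exempts an admission, not the event behind it, so nothing stops that event from being serious. This stands for four of the five criteria. It does not settle the fifth, because under the hospitalisation criterion the admission is what makes the event serious. Three hospitals in two countries could read the sentence differently. The important-medical-event criterion helps, but it rests on individual judgement.

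It is also fair to say that excluding planned admissions as such is reasonable here. Knee surgery for continuing pain is an expected course in this population, and the protocol treats TKA as an outcome in its own right. That supports having an exemption; it does not support leaving it unqualified.

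Two stronger readings might be inferred, and the documents support neither.

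- **That an RF complication treated in a planned admission is never counted or reported as serious.** Fatal, life-threatening, disabling and important medical events remain SAEs, and every AE is recorded.
- **That surgery in the post-TKA half of the trial goes uncaptured, because of the item "At 12 months in the osteoarthritis group, we ask if a total knee arthroplasty is performed".** Restricting that item is logical, since the other population already has a prosthesis. Surgery and admissions are collected for everyone: section 7.1.2 takes them from medical records and a patient questionnaire for the cost analysis, and sections 4.2 and 5.2 require interventions to be documented. The definition of duration of pain relief also needs to know about an operation, and Appendix E asks about adverse events at T1 to T4. These data do not assign SAE status, so they leave case C open, but they remove any claim of a blind spot in one population.

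**Conclusion.** The point holds in narrow form. Section 8.2.2 does not distinguish an admission planned before consent, or for an unchanged pre-existing condition, from one scheduled because of an event that arose or worsened after treatment. Applied literally, it drops one class of event from the SAE definition: treatment-related events whose only serious feature is a scheduled admission. For that class METC reporting, the SAE count and the top severity grade are all lost together.

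This rests on sites applying the bullet as written. The documents give no rate for such events, so no frequency or effect on the SAE proportions can be estimated. The wording is the same for both arms, and all between-arm testing is exploratory. The primary endpoint, sample size and non-inferiority comparison are unaffected. This is a minor gap in safety reporting that is cheap to close.

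**What to change.** Reword the closing bullet of section 8.2.2 so that it agrees with the hospitalisation criterion. Suggested text:

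*A hospital admission planned before consent, or for a pre-existing condition that has not worsened since consent, is not in itself a serious adverse event. An elective admission arranged because of an adverse event that arose or worsened during the study is assessed against the criteria above.*

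The Severe grade in section 8.2.1 then follows without further change, since it refers back to SAE status. No new question or visit is needed, because surgery and admissions are already documented in all patients. The cost is one sentence, notified to the METC as an amendment under section 11.2, plus a few more admissions to assess and, where they qualify, report.
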